10.1 INCLUSION CRITERIA

- 1. Healthy subjects of both sexes with an age \geq 18 and \leq 50.
- 2. ASA classification 1
- 3. Positive Allen's test
- 4. Intact and healthy skin on the selected wrist
- 5. Wrist circumference between 150 mm e 200 mm.
- 6. Normal ECG obtained at screening or within 2 months prior to screening
- 7. Ability to understand and execute the required study procedures and provide an informed consent to the study.

10.2 EXCLUSION CRITERIA

1. Presence of at least one of the following altered hemoglobin parameters at screening:

Clinical Investigational Plan Version 1.0 Page 24 of 45 01M2020-CH.LMD Date: 22 December 2020

- a. $\alpha Hb \leq 10 \text{ gr/dl}$
- b. COHb ≥ 3%
- c. MetHb ≥ 2%
- 2. For pre-menopausal female subjects only: positive pregnancy test performed at screening on urines or capillary blood
- 3. Presence of any cardiovascular pathology in medical history

Protocol No.:

- 4. Any episodes of respiratory infection during the 30 days prior to screening
- 5. Any prior experience of dyspnea
- 6. Hospitalization during the 2 months prior to screening, for any reason.
- 7. Chronic drug intake known to interfere with gaseous exchanges or induce changes in cardiac frequency
- 8. Presence of any medical condition not allowing the subject to perform the required test
- 9. Known allergy to adhesive tapes
- 10. Participation in an interventional study with a medicinal product or a medical device in the 30 days prior to screening.

10.3 POINT OF ENROLLMENT

Point of enrollment is defined as the point where the subject, after having signed the informed consent form, is confirmed to fulfill all criteria for eligibility.

Following the point of enrollment, each subject will undergo study procedures and measurements.

10.4 WITHDRAWAL/DISCONTINUATION FROM THE STUDY

Subjects may choose not to participate in the study or to withdraw from the study at any time by informing the Investigator. Participation in the clinical investigation is entirely voluntary.

Subjects' participation in the study will be terminated early by the Investigator in the following situations:

- Study is terminated by the investigator/Sponsor
- For other reasons, e.g. repeated protocol violations or inability to meet protocol requirements, at Investigator's discretion

Sponsor should be informed of all subjects whose participation in the study is terminated early.

Subjects who are withdrawn from the study due to adverse events (AE), on the basis of Investigator's judgement, will be followed until medical condition returns to baseline, or is considered stable, and will be recorded in the Case Report Form (CRF).

All subjects enrolled in the clinical investigation (including those withdrawn early from the clinical investigation) shall be accounted for and documented.

Clinical Investigational Plan			
Protocol No.:	Version 1.0	Page 25 of 45	
01M2020-CH.LMD	Date: 22 December 2020	. 480 10 01 10	

10.5 PROCEDURE FOR SUBJECT REPLACEMENT

Should there be circumstances not allowing to proceed with the experimental protocol, for whatever reason, related to subject's reaction or to the poor quality of the photoplethysmographic signals recorded and verified in real time (see Section 11), the following steps shall be followed:

- The actual interruption of the clinical protocol for that subject will be registered on the subject's CRF, noting the reasons;
- Any "valid" measurement collected before study interruption will be kept (see Section 17 for a definition of "valid measurement");

Please note that, based on minimum data requirements for the study, it is possible that up to 2 additional subjects may need to be enrolled in order to reach the established number of target measurements (see Section 3).

10.6 EXPECTED STUDY DURATION

Expected duration for each subject is approximately two weeks from screening up to completion of test session. The test session is expected to last approximately 50 minutes (including subject and equipment preparation, measurement session and final subject status verification).

Total duration of the study is expected to be about 3 weeks from first subject enrolled until last subject completed.

11 STUDY PROCEDURES

A schematic representation of the procedures performed in the study is shown below in Table 2:

Procedures	Screening Visit	Visit 1 - Test session (Within 2 weeks from Screening)
Informed Consent	Х	
Medical history	Х	
ECG	Х*	
Physical exam (including wrist skin evaluation)	Х	
Skin Pigmentation assessment (Fitzpatrick scale)	Х	
Wrist circumference measurement	Х	
ASA classification	Х	
Vital signs	Х	X§
Allen test	Х	

Cli	nical Investigational Plan		
	Version 1.0	Page 26 of 45	

Χ

Date: 22 December 2020

Procedures	Screening Visit	Visit 1 - Test session (Within 2 weeks from Screening)
Concomitant medications	Х	
Blood test for Hb parameters	Х	
Pregnancy test (urinary or capillary blood)	X**	
Inclusion/exclusion criteria assessment	Х	
BrOxy M recording		Х
Reference device recording		x

Table 2: Study flowchart

Adverse Events

The following sections include a detailed description of study procedures at each visit.

Protocol No.:

01M2020-CH.LMD

11.1 SCREENING VISIT (FROM DAY -14 TO DAY 0)

11.1.1 Informed consent

Informed consent shall be obtained in writing from each subject. The subject will sign and personally date the informed consent form attesting that the information was accurately explained and that informed consent was freely given. The original signed informed consent form will be kept in the site file and a copy will be given to the patient.

The process of obtaining the informed consent shall be documented before any procedure specific to the study is applied to the subject.

11.1.2 Eligibility assessment

Subjects will be assessed for eligibility and all inclusion/exclusion criteria will be verified.

Demographic data and medical history of past or present cardiovascular or pulmonary illnesses as well as information on medication currently being taken to address current illnesses will be obtained by the investigator.

Patients will be permitted to receive concomitant therapy as medically required. A record of all concomitant prescription medications will be maintained. Subjects undergoing drug treatments known to interfere with gaseous exchanges or cardiac frequency will be excluded.

A physical examination will be performed which will include the examination of general appearance and body systems as indicated by patient symptoms, with particular attention to the wrist skin. The subject

^{§ 5} minutes after end of test session

^{*} ECG required at screening unless a 12-lead ECG has been performed in the last 2 months prior to screening

^{**}pregnancy test only for pre-menopausal women.

Clinical Investigational Plan			
Protocol No.:	Version 1.0	Page 27 of 45	
01M2020-CH.LMD	Date: 22 December 2020	Page 27 01 43	

will be asked about any known reaction/allergy to any of the device components. Subjects will be assessed for ASA classification and Allen's test.

Systolic/diastolic blood pressure will be recorded after 5 minutes of rest. Wrist circumference will be measured. Skin pigmentation will be measured using the Fitzpatrick scale (see Appendix A).

A 12 lead ECG will be performed (unless the subject had an ECG tracing done in the last 2 months) and blood sample taken to assess hemoglobin parameters (aHb; COHb and MetHb).

For pre-menopausal females a urine or capillary blood pregnancy test will be obtained.

All measurements will be recorded in the CRF.

Once all screening tests/assessments are completed the subject will be determined to be eligible or excluded.

11.2 VISIT 1 – TEST SESSION (DAY 1)

The study involves, starting from medical air (O2 concentration 20.98%), the subsequent use of cylinders with an oxygen concentration of 15%, 13% and 11%, rest nitrogen. We will use a Hans Rudolph one-way valve connected to the subject with a nose piece to eliminate nasal ventilation and with a disposable mouthpiece and filter. The valve on the inhalation side will be connected, with a two-way tap, to a Douglas bag supplied by the gas cylinder with a concentration selected according to the target level of SpO_2 to be obtained (see Table 1).

From each session of measurements on each subject, the photoplethysmographic signals in the red and infrared frequency will be collected from the subject's wrist, while the comparison measurements will be carried out using the reference oximeter.

As shown in Figure 1, during the execution of the protocol, four different saturation plateaus will be used (in steps of 5% and, therefore, at 97%, 92%, 87% and 82%), waiting 30" before starting to keep the SpO₂ level on each plateau for 2.5' in order to obtain 8 measurements in post-processing. These measurements will be at least 20" away from each other, for a total of 32 measurements for each subject as summarized in Table 1 (on page 17 and replicated below).

Plateau no.	Range SpO₂ (%)	Inhaled solution	Plateau duration	N. of Measurements of SpO ₂ and HR extracted from recordings
1)	95 – 100 (target 97%)	Ambient air (medical air)	2.5'	8
II)	90 – 94 (target 92%)	O2 15% + N 85%	2.5'	8
III)	85 – 89 (target 87%)	O2 13% + N 87%	2.5'	8
IV)	80 – 84 (target 82%)	O2 11% +N 89%	2.5'	8
			Total	32 measurements

Clinical Investigational Plan			
Protocol No.:	Version 1.0	Page 28 of 45	
01M2020-CH.LMD	Date: 22 December 2020	rage 28 01 43	

Table 1: Number of measurements to be performed for each subject, for each target level of SpO₂ and indication of the gaseous solution inhaled during each target level.

[figure not shown]

Figure 1: Time distribution of the SpO_2 measurements to be carried out on each individual subject. Four different saturation plateaus will be used, waiting the plateau stabilization before starting the 2.5' signal recording from which the series of 8 measurements with at least 20' of pause are extracted by means of a post-processing algorithm.

Before starting the measurement protocol, as shown in Figure 1, in order to prepare the above instrumentation, it is necessary to carry out the following operations:

- 1. Start the PC;
- 2. Start the reference pulse oximeter device for monitoring the SpO₂ and HR on the subject's left index:
 - Verify that the registration of SpO₂ and HR measurements is effective;
 - Verify that the safety alarms are active and correctly set;
 - Verify that the clock of the reference device is consistent with the time shown on the PC clock used to manage BrOxy M.
- 3. Connect the medical power supply of BrOxy charging base to the power outlet;
- 4. Connect the medical power supply to the charging base;
- 5. Connect the charging base to the PC via the USB cable;
- 6. Place the BrOxy M wearable device on the charging base;
- 7. Start the "BrOxy software" by double clicking on the icon on the desktop and log in with your account.

Subject preparation (see figure 5):

- The subject will be invited to sit in in a comfortable position and breathe normally
- The subject will be asked to move as little as possible during the test and to notify the Investigator immediately in case of any adverse event suffered during the test

Clinical Investigational Plan			
Protocol No.:	Version 1.0	Page 29 of 45	
01M2020-CH.LMD	Date: 22 December 2020		

- On the BrOxy software GUI, follow the procedure for inserting a new medical record (see User Manual, par. 14.3.1), entering only requested personal data according to the following scheme:
 - Last name: enter the patient code used for the registration;
 - Name: enter again the patient code
 - Date of birth: enter the date of birth of the patient;
 - Weight, height, etc.: leave the fields blank.
- Carry out the procedure for the assignment of a device (see User Manual, par. 14.4.1), following the steps provided for by the software.
- The subject is made to wear nose clip, the respiratory mask with filter correctly connected to the
 circuit for the administration of the gaseous solution with controlled oxygen concentration
 (starting from standard conditions).

[figure not shown]

Figure 5: Experimental setup to be used during the measurements.

The test protocol on the single subject will then be started. Detailed instructions will be provided to the Investigators in writing and during training sessions performed prior to study start.

After 5 minutes following test completion blood pressure will be measured and if no abnormalities are recorded, the subject will officially leave the study.

In case of abnormalities the subject will be followed-up until resolution and return to a "normal state".

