The study protocol follows the requirements of the standard ISO 80601-2-61:2017 "Medical electrical equipment - Part 2-61: particular requirements for basic safety and essential performance of pulse oximeter equipment". As such, in this study BrOxy M and the reference device will be tested on healthy volunteers accepting to participate in a controlled desaturation study. Use of both devices will be in accordance with the limitations imposed by and instructions included in the BrOxy M and Reference device User Manual.

Due to the use of a controlled desaturation protocol foreseen by the standard ISO 80601-2-61:2017, this study is classified as an interventional post-market clinical study in accordance with Annex I of EN ISO 14155:2020.

Clinical Investigational Plan		
Protocol No.:	Version 1.0	Page 15 of 45
01M2020-CH.LMD	Date: 22 December 2020	

During the execution of the protocol, the following measurements will be acquired in continuous mode:

- 1) the SpO₂ and HR values from the reference device, and
- 2) the photoplethysmographic signals with BrOxy M.

As shown in Figure 1, the protocol provides for the maintenance of 4 plateaus at 4 different values of saturation in steps of 5% and, therefore, at 97%, 92%, 87% and 82% SpO_2 . The SpO_2 value displayed on the reference device will be used to check the saturation level reached during each plateau level. For each level, at least 30" will be expected in order to stabilize the SpO_2 value and, subsequently, the plateau will be maintained for 2.5', continuing the parallel acquisition with both the reference device and BrOxy M.

[figure not shown]

Figure 1: Time distribution of the SpO₂ measurements to be carried out on each individual subject.

Four different saturation plateaus will be used, waiting for the plateau stabilization before starting the 2.5' signal recording from which the series of 8 measurements with at least 20' of pause are extracted by means of a post-processing algorithm.

After data acquisition, up to 8 measurements for SpO₂ and HR will be selected from each plateau as follows:

- Reference device: SpO₂ and HR values will be selected starting from at least 30" after plateau stabilization, with a time interval between measurements of at least 20".
- BrOxy M: SpO₂ and HR values generated by BrOxy M will be obtained by processing the
 photoplethysmographic signals generated by the device with the BrOxy Medical software. Then,

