- Bland -Altman (B&A) plot, to evaluate the agreement between experimental and standard values; the B&A plot analysis is a simple way to evaluate a bias between the mean differences, and to estimate an agreement interval, within which 95% of the differences of the second method, compared to the first one, fall. Data can be analyzed both as unit differences plot and as percentage differences. The Bland-Altman chart is a scatterplot with the difference of the two measurements for each sample on the vertical axis and the average of the two measurements on the horizontal axis. Three horizontal reference lines are superimposed on the scatterplot one line at the average difference between the measurements, along with lines to mark the upper and lower control limits of plus and minus 1.96*the standard deviation of the measurement differences. Bland and Altman also discuss the option of using confidence interval bounds, based on the standard error of the mean, for the upper and lower reference lines. If the two methods are comparable, then differences should be small, with the mean of the differences close to 0, and show no systematic variation with the mean of the two measurements. 'Small' would be an amount that would be clinically insignificant for the factor being measured.

Clinical Investigational Plan			
Protocol No.:	Version 1.0	Page 36 of 45	
01M2020-CH.LMD	Date: 22 December 2020		

• Linear regression analysis: to give further information about any potential proportional bias about the mean differences and averages. It is a simple test for a linear trend, with the mean difference as dependent variable and the average difference as independent. The aim is to evaluate if the mean difference can be predicted from the average. The resulting coefficients indicate whether one can accept the null hypothesis that there is no proportional bias.

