17.3 DATA PROCESSING

Subject's data from the paper CRF will be entered manually on an electronic clinical database.

Measurements obtained with the reference device and with BrOxy M will be accessed by the Sponsor Data Manager, and processed as follows. After data acquisition from the devices, first 8 valid paired assessments of SpO_2 and HR will be selected from each plateau as follows:

- Reference device: SpO₂ and HR valid values will be selected starting from at least 30" after plateau stabilization, with a time interval between measurements of at least 20".
- BrOxy M: SpO₂ and HR values generated by BrOxy M will be obtained by processing the
 photoplethysmographic signals generated by the device with the BrOxy Medical software. Then,
 SpO₂ and HR values corresponding to the same time points selected for the reference pulse
 oximeter will be chosen.

As a result, it is expected that up to 32 paired (and synchronized) measurements of SpO₂ and HR will be obtained from each enrolled subject, from the reference device and BrOxy M. Once paired measurements for SpO₂ and cardiac frequency have been obtained at the preselected time points (0, 20", 40", etc.) the list of paired observations will be merged with subject's data in the clinical database.

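### In the visible text the plateaus run in one descending order and pairs come only from them, so a trend in error across saturation cannot be attributed to saturation rather than to a shift over the session

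*Combined protocol and SAP*

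**What the plan says.** Section 11.2 gives one sequence: medical air first, then "the subsequent use of cylinders with an oxygen concentration of 15%, 13% and 11%, rest nitrogen". The targets are 97, 92, 87 and 82% SpO₂. The caption of Figure 1 says its time distribution is "to be carried out on each individual subject". No reversed, randomised or repeated order appears in the visible text.

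Readings come only from those plateaus. Section 11.2 plans 8 per plateau, "for a total of 32 measurements for each subject as summarized in Table 1", and Section 17.3 takes the first 8 "valid paired assessments of SpO_2 and HR will be selected from each plateau as follows". Room air appears once, as plateau I. For the end of the session, Section 11.2 says "After 5 minutes following test completion blood pressure will be measured"; no closing SpO₂ pair is planned.

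For error that varies with saturation, Section 16.3.2 plans a linear regression of the difference on the average: "The aim is to evaluate if the mean difference can be predicted from the average". Neither this model nor any other planned analysis contains time or plateau order, and drift is not discussed.

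**The concern.** In every subject, lower saturation also means longer on the wrist and later in the session. If the difference between the devices moves over the session, for example through sensor warming, adhesive contact or perfusion, the planned regression cannot tell that movement from error that depends on saturation. A shift could create an apparent proportional bias or cancel a real one. What is at stake is the interpretation of the trend and of accuracy by level. No level is measured again later in the session to check the reading.

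**Working it through.** **Inputs from the documents.** 10 analysed subjects and 320 pairs (16.2); 4 plateaus with 8 readings each at 97, 92, 87 and 82% (Table 1); readings at least 20 s apart (17.3); 30 s stabilisation plus 2.5 min, i.e. 3 min per plateau (3, 11.2); recording for up to about 35 min (5.2, 8.2); two-sided 0.05 (16.1).

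**Assumed, not in the documents.** SD of the difference 2 points; independent readings unless stated; equally spaced plateau starts, s = 3 min (back to back, 12 min in all) or s = 32/3 min (last plateau ending at 35 min).

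1. *Plan's own figure.* 10 × 4 × 8 = 320. It reproduces.

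2. *Between plateaus.* Level falls 5 points per step and time rises s minutes per step. One is an exact linear function of the other, so r = -1.00.

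3. *Across the 32 readings.* Between-plateau variance of time is B = 1.25 s². Within-plateau variance for 8 readings 1/3 min apart is W = (1/9)(64 - 1)/12 = 0.583. Then r = -√(B/(B + W)) and VIF = (B + W)/W.
 - s = 3: B = 11.25, r = -0.975, VIF = 20.
 - s = 32/3: B = 142.2, r = -0.998, VIF = 245.
 - If SpO₂ also varies within plateaus with an assumed SD of 1 point, r is -0.96 to -0.98 and VIF 13 to 30.

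4. *Effect on the planned slope.* False slope = shift/15. A shift of 1 point from plateau I to IV gives 1/15 = 0.067 per SpO₂ point.

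5. *Could the 320 pairs separate the two?* The sum of squares of level is 320 × 31.25 = 10,000, so the slope SE is 2/100 = 0.020 per point, or 0.30 over 15 points. Adjusting for linear drift multiplies this by √VIF: 0.30 × √20.3 = 1.35 points at s = 3, and 0.30 × √244.8 = 4.69 at s = 32/3. Some information remains within plateaus, but too little to use.

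6. *What a closing air block adds.* With levels 97, 92, 87, 82, 97 in equal steps, r = -10/√(10 × 170) = -0.24 and VIF = 1.06. With 80 readings for each unit of plateau sum of squares, SE = 2/√13,600 × √1.06 = 0.0177 per point, or 0.26 to 0.27 over 15 points.

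7. *Precision of opening-to-closing change, 10 subjects.* Half-width = 2.262 × SD of change/√10.
 - Independent readings, equal drift in all subjects: SD = √(2 × 4/8) = 1.00; half-width 0.72.
 - Total SD 2 made up of subject SD 1.2, subject-by-plateau SD 1 and residual variance 4 - 1.44 - 1 = 1.56, plus between-subject drift SD 1: SD = √(2(1 + 1.56/8) + 1) = 1.84; half-width 1.32.

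8. *Illustration only.* Suppose drift of 0.05, 0.1 or 0.2 points/min at 3-min spacing. The shift is 9 times that (0.45, 0.9, 1.8), the slope 0.03, 0.06, 0.12, and slope/SE is 1.5, 3 and 6. With 320 independent pairs, about 32%, 85% and 100% of trials would report proportional bias. Under the clustering in step 7 without drift variation, the naive test flags about 21 to 24% with no drift at all, and a subject-level test flags about 14% at the lowest rate.

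9. *Room in the wait.* Eight readings 20 s apart span 140 s, which leaves 300 - 140 = 160 s of the 5 minutes for the reference to return to the plateau I range.

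**The case against.** **The session may not be a plain staircase.** Figure 1 is not shown, and detailed test instructions are issued separately (11.2). Recording lasts up to about 35 min against 12 min of plateaus. Section 8.2 limits continuous time below 90% to 3 min, whereas plateaus III and IV back to back would take 6. Returns to air are plausible, and since recording is continuous (Section 3) such signal may exist. This stands: a reader might infer that subjects never return to air, and the documents do not support that. It does not rescue the planned analysis, because Section 17.3 selects no readings from such intervals. Section 16.2 might also suggest a fifth air block, since 80 in air plus 80 at each of four levels is 400. But that contradicts its own total of 320, so it does not establish one.

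**The primary result is little affected.** Drift in use is device error and belongs in the bias and limits of agreement. Section 16.3.2 offers the regression as supplementary, and no acceptance criterion rests on it. This stands.

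**Drift size is unsupported.** The documents give no evidence of drift. BrOxy M is meant for recordings up to 24 h, and 0.05 to 0.2 points/min sustained for 1,440 min would be 72 to 288 points, so only a short transient could run at such rates. This stands against reading the rates in step 8 as findings. The confounding itself does not depend on drift size.

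**The remedy is limited.** It checks only near 97%, follows hypoxia and so includes any carry-over, and cannot say which device moved. An assumed drift of 0.05 points/min gives 0.05 × 12 = 0.6 points at the closing set, less than the half-width, and would usually be missed. All of this stands, and it limits what the check can claim.

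**The standard may fix the order.** That cannot be checked from the documents. The remedy leaves the order alone.

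**Conclusion.** The point holds as a limit on interpretation. As planned in the visible text, a trend from the Section 16.3.2 regression cannot be attributed to saturation rather than to a shift over the session in either device. The aliasing is exact between plateaus and nearly complete across readings (VIF about 20 to 245, depending on the assumed spacing). Each point of shift between plateaus I and IV moves the slope by 0.067.

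A reader might go further in three ways that the documents do not support:
- That drift and saturation are wholly inseparable. Within-plateau trends carry a little information, with an SE of 1.35 to 4.7 points over the range at an assumed SD of 2.
- That the accuracy result is invalid. Pooled bias and limits of agreement already include any drift.
- That the wrist sensor is known to drift. Nothing in the documents shows this, and drift in the finger reference would be confounded in the same way.

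This is an inexpensive improvement to the plan, not a defect that undermines the primary comparison.

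**What to change.** - **Section 11.2:** keep both devices in place and recording through the existing 5-minute wait, and ask the subject to stay still.
- **Section 17.3:** once the subject is on air and the reference is back in the plateau I range, extract up to 8 closing pairs by the existing validity and spacing rules. Treat any air intervals recorded between plateaus in the same way.
- **Section 16.2:** keep these pairs out of the 320, so that they do not dilute the low range.
- **Section 16.3.2:** report the within-subject change in bias from opening to closing air, with a 95% CI from subject-level means, and interpret the regression trend in its light. State that the check applies near 97%, includes any carry-over after hypoxia, and does not identify the device. If closing pairs are not obtained, state that the trend cannot be attributed to saturation alone.

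The cost is a few more minutes of recording inside a wait already planned, one more table, and an update of the stated recording time if it is exceeded. No further hypoxia is involved, and the gas sequence is unchanged.
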